3.3 Exploratory Objective(s)

- (1) **Objective:** To evaluate key biomarkers (via tumor biopsy and peripheral blood sample) at baseline and 10-14 days after administration of oral dabrafenib and/or trametinib in combination with intravenously administered pembrolizumab, and determine the relationship between key biomarkers and clinical response.
- (2) **Objective:** To evaluate key biomarkers (via tumor biopsy and peripheral blood sample) at the time of progression after administration of oral dabrafenib and/or trametinib in combination with intravenously administered pembrolizumab, and determine the relationship between key biomarkers and clinical progression.
- (3) **Objective:** To evaluate the use of tumor kinetic parameters including time to growth (TTG) modeling and simulation to evaluate the effect of pembrolizumab administered intravenously in combination with oral dabrafenib and trametinib in subjects with advanced (unresectable or metastatic) melanoma with BRAF V600 E or K mutations. These tumor kinetics parameters may be correlated with clinical outcomes.
- (4) **Objective:** To evaluate the efficacy of pembrolizumab administered intravenously in combination with oral dabrafenib and trametinib in subjects with advanced (unresectable or metastatic) melanoma with BRAF V600 E or K mutations with respect to Best Overall Response, 5-Category Best Overall Response, 5-Category Ordinal Response by Week, Percentage of Subjects with Complete Response, Percentage of Subjects with Partial Response, Percentage of Subjects with Deep Response, Best

Target Lesion Response, Time to Confirmed Response, Percentage of Subjects with Sustained Response at Week 36 (see Section 8.2.3.1 for endpoint definitions), EuroQol (EQ-5D), and EORTC (QLQ-C30) compared with oral dabrafenib and trametinib alone in Part 3.

- (5) **Objective:** To evaluate the potential for development of anti-drug antibodies (ADA) after administration of pembrolizumab.

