6.0 TRIAL FLOW CHART

6.1 Treatment Phase

6.1.1 Parts 1 and 2: Pembrolizumab Q3W Dosing with Trametinib and/or Dabrafenib

Trial Period:	Screening ⁹	Treatment (6-Week Cycle)										End of Treatment
Visit Number:	1	2	3	4	5	6	7	8	9	≥ 10	Discontinuation ²³	
Days	(-28 to -1)	1	8	15	22	29	36	1	22	1,22		
Cycle		1						2		≥ 3		
Scheduling Window (Days)		±3	±3	±3	±3	±3	±3	±3	±3	±3		
Administrative Procedures												
Informed Consent ¹	X											
Informed Consent for Future Biomedical Research (optional)	X											
Inclusion/Exclusion Criteria	X											
Subject Identification Card	X											
Demographics and Medical History ²	X											
Prior and Concomitant Medication Review ³	X	X	X	X	X	X	X	X	X	X	X	
Treatment Assignment		X										
Survival status ²⁸		←----->										
Clinical Procedures / Assessments												
Full Physical Examination ²⁷	X	X						X		X ²⁴		
Directed Physical Examination			X	X	X	X	X	X	X	X ²⁴	X	
Vital Signs and Weight ⁴	X	X	X	X	X	X	X	X	X	X	X	
12-Lead Electrocardiogram (ECG) ⁵	X	X						X		X ²⁵		
ECHO	X					X				X ²⁵		
Review Adverse Events ^{6,7,8}		X	X	X	X	X	X	X	X	X	X	
ECOG Performance Status	X	X						X		X ²⁵	X	

Trial Period:	Screening ⁹	Treatment (6-Week Cycle)									End of Treatment
Visit Number:	1	2	3	4	5	6	7	8	9	≥ 10	Discontinuation ²³
Days	(-28 to -1)	1	8	15	22	29	36	1	22	1,22	
Cycle		1						2		≥ 3	
Scheduling Window (Days)		±3	±3	±3	±3	±3	±3	±3	±3	±3	
Laboratory Procedures / Assessments⁹											
Pregnancy Test - Urine or Serum β-HCG ¹⁰	X										
CBC with Differential ¹¹	X	X	X	X	X	X	X	X	X	X ²⁵	X
Comprehensive Chemistry Panel ¹¹	X	X	X	X	X	X	X	X	X	X ²⁵	X
Urinalysis ¹¹	X	X	X	X	X	X	X	X	X	X ²⁵	X
PT/INR and aPTT ¹²	X	As clinically indicated									
Calculated Creatinine Clearance	X										
T3, FT4 and TSH ^{11,13}	X	X						X		X ¹³	X
Hepatitis B and C ¹⁴	X										
Blood for Future Biomedical Research ¹⁵ (optional)		X									
Drug Dispensation, Administration, and Associated Analyses											
pembrolizumab Administration (30-minute infusion)		X			X			X	X	X	
Pharmacokinetics of pembrolizumab ¹⁶		X			X			X		X ²⁵	
Anti-pembrolizumab Antibodies ¹⁷		X						X		X ²⁵	
Dispensation of Drug Kit		X			X			X	X	X ²⁵	
Pharmacokinetics of Dabrafenib and/or Trametinib ¹⁸					X			X		X ²⁵	X
Efficacy Measurements											
Tumor Imaging ¹⁹	X									X ²⁵	X
Tissue Collection and Pharmacodynamic Assessment											
BRAF Testing ²⁰	X										
Tumor Tissue Collection ²¹	X		X ²¹								X ²⁶
Correlative Blood Sample ²¹	X	X						X			X

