21 In order to be eligible for the study, all subjects must provide a tumor tissue specimen for biomarker analysis and blood samples for pharmacodynamic assessment. The tissue specimen may be collected any time from the initial diagnosis to the study entry and may be an archival tissue sample (within 90 days of Study Day 1=first dose(s) of study treatment) if it is not feasible to obtain a fresh biopsy not previously irradiated. Site documentation that the sample has been shipped to the biomarker analysis laboratory is sufficient evidence to meet eligibility criterion. If a tumor biopsy was obtained of a target lesion during eligibility assessment, it is preferred to obtain a new baseline scan. Biopsy of lesions on study should be limited to non-target lesions or new lesions if their pathologic etiology is ambiguous. The tissue sample should have proper size to enable multiple planned biomarker analyses, but not artificially decrease the longest diameter of the lesion. Additionally, a fresh biopsy should be obtained 10-14 days following initiation of study treatment for Parts 1 and 2 of the study. The fresh biopsy at 10-14 days following initiation of study treatment is optional in Part 3 of the study. Detailed instructions for blood sample collection, tissue collection, processing and shipment are provided in the Laboratory and Procedures Manual, respectively. Any leftover blood or tumor tissue may be stored for future research if the subject signs the optional FBR consent.

22 Blood for genetics sample will be collected to explore host genetics and to identify genetic predictors which may have a role in therapeutic response to pembrolizumab.

23 The discontinuation visit should be scheduled at the time of permanent discontinuation of all treatments (pembrolizumab, trametinib, and/or dabrafenib). The window for this visit is +10 days. Required assessments for this visit are identified in the study flow chart; additional assessments that are not flagged as required may be performed if clinically indicated (e.g., coagulation tests, thyroid function tests, etc.).

24 Perform a full physical examination on the first day of each cycle and a directed physical examination on Day 22 of each cycle. Example: full physical exam on C3D1, directed physical exam on C3D22, full physical exam on C4D1, directed physical exam on C4D22, etc.

25 Day 1 and 22 of Cycle 3: CBC with Differential, Comprehensive Chemistry Panel, Urinalysis

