- 20 BRAF mutation testing is only required for melanoma subjects; BRAF mutation testing is not required for solid tumor subjects. BRAF V600 E or K mutation analysis should be performed by sites during screening in subjects without documented BRAF status. This specimen may be collected any time from the initial diagnosis to the study entry and may be an archival tissue sample (within 6 months of study entry). BRAF analysis may be performed at a local laboratory, provided that the methodology is able to detect V600E and/or V600K mutations. A sample from the originally-tested tissue block must be collected and stored at the central laboratory for possible assay at a later date (i.e., in the event that BRAF status must be confirmed). Detailed instructions for tissue collection, processing and shipment are provided in the Procedures Manual.
- 21 In order to be eligible for the study, all subjects must provide a tumor tissue specimen for biomarker analysis and blood samples for pharmacodynamic assessment. The tissue specimen may be collected any time from the initial diagnosis to the study entry and may be an archival tissue sample (within 90 days of Study Day 1=first dose(s) of study treatment) if it is not feasible to obtain a fresh biopsy not previously irradiated. Site documentation that the sample has been shipped to the biomarker analysis laboratory is sufficient evidence to meet eligibility criterion. If a tumor biopsy was obtained of a target lesion during eligibility assessment, it is preferred to obtain a new baseline scan. Biopsy of lesions on study should be limited to non-target lesions or new lesions if their pathologic etiology is ambiguous. The tissue sample should have proper size to enable multiple planned biomarker analyses, but not artificially decrease the longest diameter of the lesion. Additionally, a fresh biopsy should be obtained 10-14 days following initiation of pembrolizumab study treatment for Parts 4 and 5 of the study. Detailed instructions for blood sample collection, tissue collection, processing and shipment are provided in the Laboratory and Procedures Manual, respectively. Any leftover blood or tumor tissue may be stored for future research if the subject signs the optional FBR consent.
- 22 Blood for genetics sample will be collected to explore host genetics and to identify genetic predictors which may have a role in therapeutic response to pembrolizumab

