8.2.5.3 Biomarker Analysis

In Parts 1, 2, 4, and 5, the key biomarker will be the PD-L1 expression measured using 0-5 Allred Proportion Scores (APS) for PD-L1 staining in melanoma using the Dako assay. The mean change from baseline to Day 10-14 after administration of oral dabrafenib and/or trametinib in combination with intravenously administered pembrolizumab in PD-L1 expression will be estimated and the 95% CI for the change will be provided.

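### Parts 1-2 and 4-5: the flow-chart grids mark the on-treatment biopsy 7 days after start while the footnotes and the SAP require 10-14 days, and no correlative blood sample is scheduled at 10-14 days

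*Combined protocol and SAP*

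**What the plan says.** - **Objective.** Section 3.3, exploratory objective (1): "To evaluate key biomarkers (via tumor biopsy and peripheral blood sample) at baseline and 10-14 days after administration of oral dabrafenib and/or trametinib". The drugs are those given alongside pembrolizumab, and the objective names two specimen types, tumor and blood.
- **Rationale.** Section 4.2.3.5 repeats the 10-14 day timing for tumor tissue and makes tumor and blood samples required in Parts 1, 2, 4 and 5 but optional in Part 3.
- **Analysis.** SAP Section 8.2.5.3, for Parts 1, 2, 4 and 5: "the key biomarker will be the PD-L1 expression measured using 0-5 Allred Proportion Scores", with this estimand: "The mean change from baseline to Day 10-14 after administration of oral dabrafenib and/or trametinib" given together with pembrolizumab, reported with a 95% CI. No blood marker is named.
- **Footnotes.** Footnote 21 to 6.1.1 reads: "a fresh biopsy should be obtained 10-14 days following initiation of study treatment for Parts 1 and 2 of the study". Footnote 21 to 6.1.3 and to 6.1.4 counts from the first pembrolizumab dose instead: "a fresh biopsy should be obtained 10-14 days following initiation of pembrolizumab study treatment for Parts 4 and 5 of the study".
- **Grids.** The "Tumor Tissue Collection" row has its on-treatment mark under Day 8 in 6.1.1, Day 36 in 6.1.3 and Day 22 in 6.1.4. The scheduling window in all three charts is ±3 days. The correlative blood row is marked only at screening, the first pembrolizumab day, Cycle 2 Day 1 and discontinuation.

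**The concern.** Section 2.1 makes the Trial Flow Chart the place where procedure times and visit windows are set. In these three charts the grid and its own footnote give different times for the same invasive, required procedure. Neither is said to take precedence, and Section 8.2.5.3 has no rule for biopsies taken outside Day 10-14.

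If sites split between the two instructions, the mean PD-L1 change labelled Day 10-14 would mix biopsies from about one week and about two weeks on combination, in cohorts that are small by design. Some subjects would undergo a biopsy at a time that the plan does not analyse.

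Blood is a separate matter. There the grid does not conflict with a footnote; the timepoint named in the objective is simply not scheduled.

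**Working it through.** The plan gives no numerical figure to reproduce here. The check is to place each mark in its column and compare its visit window with the 10-14 day target.

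**Inputs.** The start is Day 1 in 6.1.1. Table 9 puts the first pembrolizumab dose at Day 29 with the 4-week run-in (6.1.3) and Day 15 with the 2-week run-in (6.1.4). The biopsy marks are Day 8, Day 36 and Day 22, and the window is ±3 days.

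**Formulas.** Visit window = mark − 3 to mark + 3, which is 7 days. Target by elapsed count = start + 10 to start + 14. Target with the first dose counted as Day 1 = start + 9 to start + 13.

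| Chart | Start | Mark (elapsed) | Visit window | Elapsed target and overlap | First-dose-is-Day-1 target and overlap |
|---|---|---|---|---|---|
| 6.1.1 | Day 1 | Day 8 (7) | Days 5-11 | Days 11-15: Day 11 | Days 10-14: Days 10, 11 |
| 6.1.3 | Day 29 | Day 36 (7) | Days 33-39 | Days 39-43: Day 39 | Days 38-42: Days 38, 39 |
| 6.1.4 | Day 15 | Day 22 (7) | Days 19-25 | Days 25-29: Day 25 | Days 24-28: Days 24, 25 |

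In every chart the window runs from 4 to 10 days after start. The overlap is 1/7 = 14% of permitted days by elapsed count, or 2/7 = 29% on the other count. The nominal visit is outside the target on both.

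**Next scheduled visit.** Day 15, Day 43 and Day 29 are each 14 days after the relevant start. With the same ±3 days, the overlap is 4/7 (57%) by elapsed count (Days 12-15, 40-43 and 26-29) and 3/7 (43%) on the other count. These are clinic visits at which blood is already drawn for hematology and chemistry.

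**Blood.** The scheduled on-treatment points are the first pembrolizumab day (0 days after combination start) and Cycle 2 Day 1. Cycle 1 lasts 6, 10 or 8 weeks, so Cycle 2 Day 1 is 42 days (43 − 1), 42 days (71 − 29) and 42 days (57 − 15) after start. Samples scheduled at 10-14 days: 0 in each chart. In 6.1.4 the Day 15 sample follows 14 days of trametinib, but it falls on the first pembrolizumab day and so is not an on-combination sample.

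**The case against.** The strongest reply is that the footnote governs. In 6.1.1 the Day 8 cell itself carries reference 21; in 6.1.3 and 6.1.4 the row label does. A site that reads it will biopsy at 10-14 days. Footnotes elsewhere in these charts also set timing that the grid does not show: imaging gets ±7 days despite the ±3 header, and one PK sample is due 24-96 hours after the first pembrolizumab dose with no column of its own. In Part 3 the optional 10-14 day biopsy is marked under Day 1, which can only be a pointer to its footnote.

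This stands far enough to rule out a reading that a reader might infer, that the tissue endpoint will mostly be missed. The 14% (or 29%) is a share of calendar days for a site that follows the grid. It is not a predicted miss rate, and the documents do not show how sites behave. The reply does not remove the contradiction, because grid and footnote belong to the same governing section and disagree.

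Two further inferences also fail. The blood cannot be called unobtainable or wholly absent: baseline blood and later on-treatment blood are scheduled, and footnote 21 leaves collection instructions to manuals not available here. The gap is one unscheduled timepoint. Nor does it damage the key biomarker analysis, which is tissue PD-L1.

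The column positions come from tables extracted from PDF, so a merged cell could have collapsed to its first column. The tissue and blood rows keep the full cell count (11, 15 and 13), and all three charts put the biopsy mark 7 days after start, which makes this less likely. Some doubt remains for the biopsy marks; the blood finding does not depend on it.

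**Conclusion.** The point holds as an internal inconsistency plus one omission. In 6.1.1, 6.1.3 and 6.1.4 the grid marks the required biopsy 7 days after start, while the footnotes, objective 3.3(1), Section 4.2.3.5 and SAP 8.2.5.3 say 10-14 days. For a site that follows the grid, 1 or 2 of the 7 permitted days qualify, depending on the count. No correlative blood is scheduled 10-14 days after combination start, so that part of objective 3.3(1) has no planned sample.

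The consequence is limited. The objective is exploratory, and no dose, efficacy or stopping rule in the plan uses it. Part 3 is outside the point because its biopsy is optional and 8.2.5.3 does not cover it. The practical effect is mainly on Parts 4-5: the document history reports that no tolerable pembrolizumab plus trametinib dose was found in Part 1, in which case Section 2.1 does not open Part 2 for that doublet, and Section 5.2.5 reports that the Part 3 final analysis, downstream of the Parts 1-2 triplet work, is done.

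The conclusion assumes that the extracted column positions are right (for tissue) and that the ±3-day window applies to the biopsy when a site books by visit.

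**What to change.** 1. Reconcile grid and footnote. With 10-14 days as the intent throughout the text, move the biopsy mark to the existing visit 14 days after start: Day 15 in 6.1.1, Day 43 in 6.1.3 and Day 29 in 6.1.4. Give the biopsy its own window of −4/+0 days (Days 11-15, 39-43 and 25-29), since the general ±3 would allow up to 17 days after start.
2. Mark the correlative blood sample at the same visit.
3. State in footnote 21 and in 8.2.5.3 that the window is counted in elapsed days from the start of the combination. If the first dose is instead counted as Day 1, the nominal visit falls one day late.
4. State in 8.2.5.3 how biopsies outside the window are handled, and report the actual elapsed day of each. This also covers samples already taken.

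The cost is one additional tube at a visit where blood is already drawn, plus a flow-chart and SAP text correction. No visit or biopsy is added.

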6.1.2 Part 3: Pembrolizumab Q3W Dosing With Trametinib and Dabrafenib

Trial Period:	Screening⁹	Treatment (6-Week Cycle)^{24,25}					End of Treatment
Visit Number:	1	2	3	4	5	≥ 6	Discontinuation ²⁵
Days	(-28 to -1)	1	22	1	22	1,22	
Cycle		1		2		≥ 3	
Scheduling Window (Days)		±3	±3	±3	±3	±3	
Administrative Procedures							
Informed Consent ¹	X						
Informed Consent for Future Biomedical Research (optional)	X						
Inclusion/Exclusion Criteria	X						
Subject Identification Card	X						
Demographics and Medical History ²	X						
Prior and Concomitant Medication Review ³	X	X	X	X	X	X	X
Treatment Assignment		X					
Survival Status ³⁰		←----->					
Clinical Procedures / Assessments							
Full Physical Examination ²⁹	X	X		X		X ²⁶	
Directed Physical Examination			X		X	X ²⁶	X
Vital Signs and Weight ⁴	X	X	X	X	X	X	X
12-Lead Electrocardiogram (ECG) ⁵	X	X		X		X ²⁷	
ECHO	X		X			X ²⁷	
Review Adverse Events ^{6,7,8}		X	X	X	X	X	X
ECOG Performance Status	X	X		X		X ²⁷	X
Laboratory Procedures / Assessments⁹							
Pregnancy Test - Urine or Serum β-HCG ¹⁰	X						
CBC with Differential ¹¹	X	X	X	X	X	X ²⁷	X

Trial Period:	Screening⁹	Treatment (6-Week Cycle)^{24,25}					End of Treatment
Visit Number:	1	2	3	4	5	≥ 6	Discontinuation ²⁵
Days	(-28 to -1)	1	22	1	22	1,22	
Cycle		1		2		≥ 3	
Scheduling Window (Days)		±3	±3	±3	±3	±3	
Laboratory Procedures / Assessments⁹							
Comprehensive Chemistry Panel ¹¹	X	X	X	X	X	X ²⁷	X
Urinalysis ¹¹	X	X		X		X ²⁷	X
PT/INR and aPTT ¹²	X	As clinically indicated					
Calculated Creatinine Clearance	X						
T3, FT4 and TSH ^{11,13}	X	X		X		X ¹³	X
Hepatitis B and C ¹⁴	X						
Blood for Future Biomedical Research ¹⁵ (optional)		X					
Drug Dispensation, Administration, and Associated Analyses							
pembrolizumab Administration (30-minute infusion)		X	X	X	X	X	
Pharmacokinetics of pembrolizumab ¹⁶		X	X	X		X ²⁷	
Anti-pembrolizumab Antibodies ¹⁷		X		X		X ²⁷	
Dispensation of Drug Kit		X	X	X	X	X ²⁷	
Pharmacokinetics of Dabrafenib and/or Trametinib ¹⁸			X	X		X ²⁷	X
Efficacy Measurements							
Tumor Imaging ¹⁹	X					X ²⁷	X
Patient Reported Outcomes (PRO)							
EuroQol EQ-5D ²⁰		X		X		X	X
EORTC QLQ-C30 ²⁰		X		X		X	X

Trial Period:	Screening⁹	Treatment (6-Week Cycle)^{24,25}					End of Treatment
Visit Number:	1	2	3	4	5	≥ 6	Discontinuation ²⁵
Days	(-28 to -1)	1	22	1	22	1,22	
Cycle		1		2		≥ 3	
Scheduling Window (Days)		±3	±3	±3	±3	±3	
Tissue Collection and Pharmacodynamic Assessment							
BRAF Testing ²¹	X						
Tumor Tissue Collection ²²	X	X ²²					X ²⁸
Correlative Blood Sample ²²	X	X		X			X
Blood for Genetics ²³		X					

1 Written consent must be obtained prior to performing any protocol-specific procedure. Results of a test performed prior to the subject signing consent as part of routine clinical management are acceptable in lieu of a screening test if performed within the specified time frame (e.g. within 28 days prior to Day 1). Assign Baseline number when the study informed consent is signed.
 
2 Includes history of treatment for the primary diagnosis, including prior systemic, radiation treatment and surgical treatment, and best response to prior systemic treatments. Date of last prior cancer treatment must be documented. Radiographic studies performed prior to study entry may be collected for review by the investigator.
 
3 Prior Medications - Report all medications taken within 30 days of Visit 1 and all treatments for a prior cancer even if taken greater than 30 days prior to Visit 1. Concomitant Medications - Enter new medications started during the trial through the Safety Follow-Up visit. After the Safety Follow-Up visit, record all medications taken for SAEs and ECIs as defined in Section 7.2.
 
4 Vital signs to include temperature, pulse, respiratory rate and blood pressure. If a subject's baseline weight does not fluctuate by more than 10%, this weight can be used to calculate dose. Height will be measured at Visit 1 only.
 
5 Electrocardiogram (12-lead ECG) should be performed at Screening and post-infusion at visits indicated in the flow chart.
 
6 Adverse experiences and laboratory safety measurements will be graded per NCI CTCAE version 4.0. All adverse experiences, whether gradable by CTCAE or not, will also be evaluated for seriousness.
 
7 Any adverse experience of unknown etiology associated with trial treatment exposure should be evaluated to determine if it is possibly an Event of Clinical Interest (ECI).
 
8 Evaluate subjects for symptoms or clinical signs of non-cutaneous, new primary/recurrent malignancies before initiation of treatment, periodically during treatment, or as clinically indicated. Following discontinuation of dabrafenib, monitoring for non-cutaneous secondary/recurrent malignancies should continue for up to 6 months or until initiation of another anti-neoplastic therapy. Abnormal findings should be managed according to clinical practices.
 
9 Routine laboratory tests (chemistry; hematology) for screening should be performed within 10 days prior to the first dose of trial treatment. See Section 7.1.3 for details regarding laboratory tests
 
10 For women of reproductive potential, a urine pregnancy test will be performed within 72 hours prior to first dose of trial treatment. If urine pregnancy results cannot be confirmed as negative, a serum pregnancy test, performed by the local study site laboratory, will be required. Pregnancy tests (serum and/or urine tests) should be repeated if required by local guidelines.
 
11 After Cycle 1, lab samples can be collected up to 48 hours prior to the scheduled time point. Laboratory results must be known and acceptable prior to dosing. LDH analysis required (stratification factor). See Section 7.1.3 for details regarding laboratory tests.
 
12 Coagulation factors (PT/INR and aPTT) should be monitored closely throughout the trial for any subject receiving anticoagulant therapy.
							

13 Thyroid function tests will be performed by a central laboratory only if the local laboratory is unable to perform this service. Following Cycle 4, testing will be performed every other cycle. In countries where T3 results are not available, FT3 results may be reported.

14 Testing will be performed by the local laboratory at Screening. Hepatitis B and Hepatitis C serologies should be obtained for subjects without a known history of Hepatitis B or C. Those with a known history are ineligible. Include HCV RNA (qualitative) and HBsAg. See Section 7.1.3 for details regarding laboratory tests.

15 Informed consent for Future Biomedical Research (FBR) samples must be obtained before the DNA sample is drawn. DNA sample for analysis should be obtained predose, on Day 1 (or with the next scheduled blood draw), as the last sample drawn, on allocated subjects only, or at a later date as soon as the informed consent is obtained. This sample should only be taken once from each subject. See Section 12.2 for guidance regarding the collection and management of specimens for FBR.

16 Pre-dose and post-dose serum samples for PK of pembrolizumab will be collected on Day 1 and Day 22 of Cycle 1 and Day 1 of Cycle 2. Thereafter, only pre-dose (C_{trough}) PK serum samples are collected at Day 1 of every alternate cycle (i.e., Day 1 of Cycle 3, Day 1 of Cycle 5, etc.). All pre-dose (C_{trough}) samples should be collected within 24 hours before the start of infusion of pembrolizumab and, if blood is collected for anti-pembrolizumab antibodies, at the same time blood sample for anti-pembrolizumab antibodies is collected. All post-dose PK samples should be collected within 30 minutes after the end of infusion of pembrolizumab. One additional post-dose pembrolizumab sample should be collected between 24 and 96 hours following C1D1. Procedures for collection of samples are described in the Procedures Manual.

17 Blood for anti-pembrolizumab antibodies should be collected on Day 1 of Cycles 1, 2, 3 and every other cycle thereafter (Cycle 5, Cycle 7, etc.). During pembrolizumab treatment, all samples should be drawn within 24 hours before infusion of pembrolizumab at the same time as blood collection for pre-dose (C_{trough}) PK serum samples of pembrolizumab.

18 On C1D22, both pre-dose and post-dose plasma samples for PK of trametinib and dabrafenib will be collected. On C1D22, morning dose(s) should be withheld until after PK (pre-dose) sample has been drawn. On C1D22, post-dose PK samples for trametinib and/or dabrafenib should be drawn (1) at the same time as when the post-dose pembrolizumab PK sample is drawn (the end of infusion), and, (2) at approximately 4-6 hours post-dose. On C2D1, subjects should take their morning dose at home. A post-dose sample will be obtained during study visit. Thereafter, PK plasma samples will be collected at Day 1 of every alternate cycle (i.e., Day 1 of Cycle 3, Day 1 of Cycle 5, etc.) during study visit. If visit is in the morning, subjects will be asked to withhold their morning dose; if visit is in the afternoon, subjects will be asked to take their morning dose as usual. Procedures for collection of samples are described in the Procedures Manual.

19 The initial tumor imaging will be performed within 28 days prior to the date of allocation. Scans performed as part of routine clinical management are acceptable for use as the screening scan if they are of diagnostic quality and performed within 28 days prior to the first dose of trial treatment. CT scans are the required modality for measurable disease unless a subject has a clinical condition, e.g., severe contrast allergy. The same imaging technique has to be used for the subject throughout the study. The visit window for subsequent imaging is ± 7 days. If there is progressive disease, radiologic assessment/tumor imaging should be obtained at least four weeks from scan date for confirmation. CT timing should follow calendar days and should not be adjusted for delays in cycle starts. Response status will be assessed by the investigator. The process for collection of CT images is described in the Procedures Manual. Tumor imaging will be performed every 6 weeks (or whenever clinically indicated) starting at Week 13 while the subject remains on study therapy; after 18 months, tumor imaging will be performed every 12 weeks (or whenever clinically indicated) while the subject remains on study therapy. Per the modified RECIST 1.1 used in this protocol, if imaging shows progressive disease, the imaging assessment should be repeated at a minimum of 4 weeks later in order to confirm progressive disease as described in Section 4.2.3.1.

20 Patient Reported Outcomes (PROs) are to be administered by trained site personnel and completed electronically by subjects prior to all other study procedures in the following order: EuroQol EQ-5D first, followed by EORTC QLQ-C30. EuroQol EQ-5D and EORTC QLQ-C30 are to be performed at C1D1, C2D1, C3D1 and Day 1 of every other cycle thereafter (C5D1, C7D1, etc.) as well as the End of Treatment, and 30-day Safety Follow-up visit. Subjects that complete 24 months on trial and opt to continue dabrafenib and trametinib will not be required to complete PROs at the 30-Day Safety follow up visit. It is most relevant and strongly recommended that ePROs are administered prior to drug administration, adverse event evaluation and disease status notification.

21 BRAF V600 E or K mutation analysis should be performed by sites during screening in subjects without documented BRAF status. This specimen may be collected any time from the initial diagnosis to the study entry and may be an archival tissue sample (within 6 months of study entry). BRAF analysis may be performed at a local laboratory, provided that the methodology is able to detect V600E and/or V600K mutations. A sample from the originally-tested tissue block must be collected and stored at the central laboratory for possible assay at a later date (i.e., in the event that BRAF status must be confirmed). Detailed instructions for tissue collection, processing and shipment are provided in the Procedures Manual.

22 In order to be eligible for the study, all subjects must provide a tumor tissue specimen for biomarker analysis and blood samples for pharmacodynamic assessment. The tissue specimen may be collected any time from the initial diagnosis to the study entry and may be an archival tissue sample (within 90 days of Study Day 1=first dose(s) of study treatment) if it is not feasible to obtain a fresh biopsy not previously irradiated. Site documentation that the sample has been shipped to the biomarker analysis laboratory is sufficient evidence to meet eligibility criterion. If a tumor biopsy was obtained of a target lesion during eligibility assessment, it is preferred to obtain a new baseline scan. Biopsy of lesions on study should be limited to non-target lesions or new lesions if their pathologic etiology is ambiguous. The tissue sample should have proper size to enable multiple planned biomarker analyses, but not artificially decrease the longest diameter of the lesion. Additionally, a fresh biopsy should be obtained 10-14 days following initiation of study treatment for Parts 1 and 2 of the study. The fresh biopsy at 10-14 days following initiation of study treatment is optional in Part 3 of the study. Detailed instructions for blood sample collection, tissue collection, processing and shipment are provided in the Laboratory and Procedures Manual, respectively. Any leftover blood or tumor tissue will be stored for future research if the subject signs the optional FBR consent.

23 Blood for genetics sample will be collected to explore host genetics and to identify genetic predictors which may have a role in therapeutic response to pembrolizumab.

24 Telephone Contact at Days 8, 15, 29, and 36 of Cycle 1 only. Review Adverse Events and Concomitant Medications.

25 The discontinuation visit should be scheduled at the time of permanent discontinuation of all treatments (pembrolizumab, trametinib, and/or dabrafenib). The window for this visit is +10 days. Required assessments for this visit are identified in the study flow chart; additional assessments that are not flagged as required may be performed if clinically indicated (e.g., coagulation tests, thyroid function tests, etc.).

26 Perform a full physical examination on the first day of each cycle and a directed physical examination on Day 22 of each cycle. Example: full physical exam on C3D1, directed physical exam on C3D22, full physical exam on C4D1, directed physical exam on C4D22, etc.

27 Day 1 and 22 of Cycle 3: CBC with Differential, Comprehensive Chemistry Panel
Day 1 ONLY from C3D1 onwards: Urinalysis
Day 1 ONLY from C4D1 onwards: CBC with Differential, Comprehensive Chemistry Panel
Day 1 ONLY of every cycle (e.g., C3D1, C4D1, C5D1, etc.): ECOG Performance Status
Day 1 and 22 of every cycle (e.g., C3D1, C3D22, C4D1, C4D22, etc.): Dispensation of Drug Kit
Day 1 ONLY of every cycle (e.g., C3D1, C4D1, C5D1, etc.) until 18 months, then Day 1 ONLY of every other cycle: Tumor Imaging
Day 1 ONLY of every alternate cycle (e.g., C3D1, C5D1, C7D1, etc.): ECG, ECHO, Pharmacokinetics of pembrolizumab and/or trametinib and/or dabrafenib, Anti-pembrolizumab Antibodies testing

28 Additional optional biopsy at disease progression is highly desired when feasible. Detailed instructions for tissue collection, processing and shipment are provided in the Procedures Manual.

29 Dermatological examination will be part of full physical examination on the first day of each cycle.

30 Updated survival status may be requested by the Sponsor at any time during the course of the study. Upon Sponsor notification, all participants who do not/will not have a scheduled study visit or study contact during the Sponsor defined time period will be contacted for their survival status (excluding participants who have a death event previously recorded).

6.1.3 Parts 4 and 5: 4-Week Monotherapy Trametinib + 6-Week Treatment Cycle(s) of Pembrolizumab Q3W Dosing With Trametinib

Trial Period:	Screening ⁹	4-Week Monotherapy Trametinib + 6-Week Combination Treatment Cycle(s)													End of Treatment
		2	3	4	5	6	7	8	9	10	11	12	13	≥ 14	
Visit Number:	1	2	3	4	5	6	7	8	9	10	11	12	13	≥ 14	Discontinuation ²³
Days	(-28 to -1)	1	8	15	22	29	36	43	50	57	64	1	22	1,22	
Cycle		1										2	≥ 3		
Scheduling Window (Days)		±3	±3	±3	±3	±3	±3	±3	±3	±3	±3	±3	±3	±3	
Administrative Procedures															
Informed Consent ¹	X														
Informed Consent for Future Biomedical Research (optional)	X														
Inclusion/Exclusion Criteria	X														
Subject Identification Card	X														
Demographics and Medical History ²	X														
Prior and Concomitant Medication Review ³	X	X	X	X	X	X	X	X	X	X	X	X	X	X	X
Treatment Assignment		X													
Survival Status ³⁰		←----->													
Clinical Procedures / Assessments															
Full Physical Examination ²⁷	X	X				X						X		X ²⁴	
Directed Physical Examination			X	X	X		X	X	X	X	X		X	X ²⁴	X
Vital Signs and Weight ⁴	X	X	X	X	X	X	X	X	X	X	X	X	X	X	X
12-Lead Electrocardiogram (ECG) ⁵	X					X						X		X ²⁵	
ECHO	X									X				X ²⁵	
Review Adverse Events ^{6,7,8}		X	X	X	X	X	X	X	X	X	X	X	X	X	X
ECOG Performance Status	X	X				X						X		X ²⁵	X

Trial Period:	Screening ⁹	4-Week Monotherapy Trametinib + 6-Week Combination Treatment Cycle(s)													End of Treatment
		2	3	4	5	6	7	8	9	10	11	12	13	≥ 14	
Visit Number:	1	2	3	4	5	6	7	8	9	10	11	12	13	≥ 14	Discontinuation ²³
Days	(-28 to -1)	1	8	15	22	29	36	43	50	57	64	1	22	1,22	
Cycle		1										2	≥ 3		
Scheduling Window (Days)		±3	±3	±3	±3	±3	±3	±3	±3	±3	±3	±3	±3	±3	
Laboratory Procedures / Assessments⁹															
Pregnancy Test - Urine or Serum β-HCG ¹⁰	X														
CBC with Differential ¹¹	X	X	X	X	X	X	X	X	X	X	X	X	X	X ²⁵	X
Comprehensive Serum Chemistry Panel ¹¹	X	X	X	X	X	X	X	X	X	X	X	X	X	X ²⁵	X
Urinalysis ¹¹	X	X	X	X	X	X	X	X	X	X	X	X	X	X ²⁵	X
PT/INR and aPTT ¹²	X	As clinically indicated													
Calculated Creatinine Clearance	X														
T3, FT4 and TSH ^{11,13}	X	X				X						X		X	X
Hepatitis B and C ¹⁴	X														
Blood for Future Biomedical Research ¹⁵ (optional)		X													
Drug Dispensation, Administration, and Associated Analyses															
pembrolizumab Administration (30-minute infusion) ^{28,29}						X			X			X	X	X	
Pharmacokinetics of pembrolizumab ¹⁶						X			X			X		X ²⁵	
Anti-pembrolizumab Antibodies ¹⁷						X						X		X ²⁵	
Dispensation of pembrolizumab						X			X			X	X	X ²⁵	
Dispensation of Trametinib		X				X			X			X	X	X ²⁵	
Dosing Regimen Trametinib (cDL1, cDL2b regimens only) ²⁸		X	X	X	X	X	X	X	X	X	X	X	X	X	
Dosing Regimen Trametinib (cDL-1b, cDL-1a regimens only) ²⁹		X	X	X	X			X	X			X	X	X	
Pharmacokinetics of Trametinib ¹⁸									X			X		X ²⁵	X

Trial Period:	Screening ⁹	4-Week Monotherapy Trametinib + 6-Week Combination Treatment Cycle(s)													End of Treatment
		2	3	4	5	6	7	8	9	10	11	12	13	≥ 14	
Visit Number:	1														Discontinuation ²³
Days	(-28 to -1)	1	8	15	22	29	36	43	50	57	64	1	22	1,22	
Cycle		1										2	≥ 3		
Scheduling Window (Days)		±3	±3	±3	±3	±3	±3	±3	±3	±3	±3	±3	±3	±3	
Efficacy Measurements															
Tumor Imaging ¹⁹	X													X ²⁵	X
Tissue Collection and Pharmacodynamic Assessment															
BRAF Testing ²⁰	X														
Tumor Tissue Collection ²¹	X						X								X ²⁶
Correlative Blood Sample ²¹	X					X						X			X
Blood for Genetics ²²		X													
